6.6.1.3. Sputum bacterial results via culture

In the subset of subjects from whom the sputum will be analysed also by culture, the proportion of subjects with sputum sample positive and the number and proportion of sputum sample positive to Hi/NTHi (with or without the *H. influenzae* confirmation by PCR of the collected bacterial isolates) and Mcat by culture will be displayed at each stable visit and at each AECOPD visit together with the 95% CIs, within each treatment group, using the same method as for PCR.

Frequencies of semi-quantitative bacteriological load (few scattered, +, ++, +++), for each vaccine group will be tabulated.

The following analyses will be performed for NTHi (alone or with other bacteria), Mcat (alone or with other bacteria) and either Hi or Mcat detected by culture:

- Percentages of subjects with acquisition for each treatment group and risk ratio between groups, considering both Day 1 and Day 91 as baseline.

CONFIDENTIAL

207489 (NTHI MCAT-002)

Statistical Analysis Plan Amendment 2 FDA Final Draft

- Percentages of subjects with apparition for each treatment group and risk ratio between groups, considering Day 1 as baseline.
- Percentages of subjects with acquisition at AECOPD visit for each treatment group and risk ratio between groups, considering both Day 1 and Day 91 as baseline.
- Percentages of subjects with apparition at AECOPD visit (when negative at previous stable visit) for each treatment group and risk ratio between groups, considering Day 1 as baseline
- Frequency table for apparition (number of apparitions for each subject from Day 1), by treatment groups.

Other bacteriological pathogens

In addition to proportion of sputum positive to Hi (*H. influenza*) and Mcat (*M. catarrhalis*), also the proportion of sputum samples at pre-vaccination (Day 1), at Day 91, Day 181, Day 271, Day 361, Day 451 and at any AECOPD visit that are positive to *S. pneumoniae*, *S. aureus*, *P. aeruginosa* and other bacteria identified via culture, will be presented together with the 95% CIs.

6.6.2. Health related quality of life (QOL)

The following analysis are exploratory and a p-value <0.1 will be considered statistically significant, however 2-sided 95% CIs will be computed to show precision of estimation. All comparisons should be interpreted with caution considering that there will be no adjustment for multiplicity.

For each of the following questionnaire missing items will not be imputed and subjects with partial data will be excluded.

EXACT-PRO daily score

The EXAcerbations of Chronic pulmonary disease Tool (EXACT) constitutes of 14 items which are patient-reported outcome (PRO) via daily diary.

All EXACT-pro scores will be divided in to the following periods:

- Screening: scores collected between screening and Visit 1 (Baseline)
- Treatment: scores collected between Visit 1 and Visit 4 (i.e., 1 month post-Dose 2)
- Exacerbation: scores collected during the start date of an exacerbation until resolution.
- Follow –up: scores collected between Visit 4 (1 month post-Dose 2) until study completion (one year after - Visit 8).
- Follow-up will be also divided by 3 months sub period:
 - from Visit 4 to Visit 5 (Day 91 to Day 180)
 - from Visit 5 to Visit 6 (Day 181 to Day 270)

CONFIDENTIAL

207489 (NTHI MCAT-002)

Statistical Analysis Plan Amendment 2 FDA Final Draft

- from Visit 6 to Visit 7 (Day 271 to Day 360)
- from Visit 7 to Visit 8 (Day 361 to Day 450)

Descriptive statistics

For each subject the average score across all days, within each period is computed. The mean score will be reported as descriptive statistics within each group (i.e., vaccine and placebo). N, mean, SD, median, min and max, on the **EXACT-PRO** average scores will be tabulated during all (stable) periods and during exacerbations.

Between groups comparison

At each period and sub period the two groups will be compared using an ANCOVA model, with the baseline value (i.e., score at screening) as covariate and treatment as fixed factor.

Note: EXACT-PRO baseline score at screening will be computed as the average within-patient score collected between screening Visit and Visit 1. If fewer than 4 days scores are available, the EXACT-PRO baseline score cannot be calculated, and it will result as missing.

COPD Assessment Test (CAT)

COPD Assessment test (CAT) is a patient-completed questionnaire assessing globally the impact of COPD (cough, sputum, dyspnoea, chest tightness) on health status. It constitutes of 8 items each scoring from 1 to 5. The Total score is given by the sum of the single item scores and it ranges from 0 to 40. Higher scores denote a more severe impact of COPD on patient's life.

CAT questionnaire will be provided to all enrolled patients at Screening, Day 271 and Day 451 (end of study), and at each AECOPD visit.

Descriptive statistics

Descriptive statistics (N, mean, SD, median, Q1 and Q3, min and max) on the CAT total score (obtained as sum of the scores of 8 single items) will be reported by scheduled visits (stable visits), by AECOPD visit and by each treatment group.

Data will be also represented via line-chart for the total score at each time points (screening, Day 271, Day 415 and any AECOPD visit) together with the 95% confidence interval around the mean of the total score.

Within group change and CAT responders

For each group and at each time point (Screening, Day 271 and Day 421), the mean of total score together with SD will be reported and a pair t-test will be performed to compare screening scores with scores at Day 271 and at Day 421.

CONFIDENTIAL

207489 (NTHI MCAT-002)

Statistical Analysis Plan Amendment 2 FDA Final Draft

Moreover, the percentage of “CAT responder” subjects will be calculated at Day 271 and 421. A “CAT responder” is defined as a subject with at least a 2 units improvement (Decrease in total score) with respect to the baseline (Screening)

Between groups comparison

Differences between groups will be analysed in terms of difference in mean for each time points (Day 271 and Day 421) by one-way ANOVA model on the total scores, with vaccine group as factor.

CAT Score at AECOPD Visit

N, mean, SD, median, Q1 and Q3, min and max CAT score during AECOPD visit will be displayed according to the number and severity of AECOPD event.

St. George's Respiratory Questionnaire assessment (SGRQ-C)

The St. George's Respiratory Questionnaire (SGRQ) is composed of 76 items that are weighted to produce three component scores: Symptoms: measuring distress caused by respiratory symptoms, Activity: measuring the effect of difficulties in mobility and physical activity, and Impact: quantifying the psychosocial impact of the disease.

A “Total” score is also computed as sum from all component items score, thus providing a global estimation of the patients respiratory health. Each of these scores ranges from 0 to 100, a score of 100 indicating maximum disability [Jones, 1991]

SGRQ-C will be provided to all enrolled patients at Screening, Day 271 and Day 451 (end of study), and at each exacerbation visit.

Descriptive statistics

Descriptive statistics (N, mean, SD, median, Q1, Q3, min and max) on the SGRQ-C (total score and symptoms, activity and impacts component scores) will be reported by scheduled visits (stable visits), at each AECOPD visit and by each treatment group.

Mean score for each component (symptoms, activity and impacts) and mean total scores will be also represented via line-chart at each time points (screening, Day 271, Day 415 and any AECOPD visit) together with the 95% confidence interval around the mean.

Within group change and SGRQ-C responders.

For each group and at each time point (Screening, Day 271 and Day 421), the mean of each component score and the mean of total score together with SD will be reported and a pair t-test will be performed to compare screening scores with scores at Day 271 and at Day 421. Moreover, the percentage of “SGRQ-C responder” subjects will be calculated at Day 271 and 421. A “SGRQ-C responder” is defined as a subject with an improvement of more than 4 unit (Decrease in total score) with respect to the baseline (Screening).

CONFIDENTIAL207489 (NTHI MCAT-002)
Statistical Analysis Plan Amendment 2 FDA Final Draft**Between groups comparison**

For all components and for the total scores, differences between groups will be analysed in terms of difference in mean for each time points (Day 271 and Day 421) by one-way ANOVA model on the total scores, with vaccine group as factor.

SGRQ-C at AECOPD Visit

N, mean, SD, median, min and max, of each component scores and of total score during AECOPD visit will be displayed according to the number and severity of AECOPD event.

Use of medication to treat (AE)COPD and Healthcare utilization (HCU)

Frequency table on the number and type of healthcare utilisation (Physician's office, Visit to Urgent Care, Visit to Emergency Department, Hospitalization) during entire study period will be presented overall and by vaccine group.

Same frequency table will be also presented for two sub-periods: all HCU before 1-month after second vaccination and all HCU between 1-month after second vaccination and study end.

Frequency table on the use of medication for COPD (or AECOPD) and type (Chronic use for COPD, Chronic use for other disorders, exacerbation rescue medication) during entire study period will be presented overall and by vaccine group.

Medications will be coded using the GSKDRUG dictionary and frequencies table by GSKDRUG code will be also reported for entire study period, overall and by vaccine group.

As for HCU frequency tables will be presented also for the two sub-periods: before 1-month after second vaccination and after 1-month after second (until study completion).

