2. STUDY DESIGN

Figure 1 Study design overview

S = Screening Visit; V = Visit; PC = Phone contact; D = Day; FU = Follow-up; BS (1) = blood sample for humoral immunogenicity; BS (2) = blood sample for cell-mediated immunogenicity (CMI), this blood sample will only be collected from a sub-cohort of subjects; BS (3) blood sample for biomarkers; SP = sputum sample

The allowed maximum interval between Screening Visit and Visit 1 is 29 days. If a delay occurs for an eligible subject so that the interval exceeds 29 days, some study procedures performed during the Screening Visit needs to be repeated within 7 days (see Table 6 of the protocol for more details).

* An AECOPD visit should be scheduled as soon as possible after the onset of AECOPD symptoms (max 96 hours after and, if applicable, preferably before starting treatment with antibiotics) During this visit blood and sputum samples will be collected. In addition, follow-up phone call(s) and/or visit(s) will take place to determine the end of the AECOPD. These contacts will take place at least every 2 weeks until the AECOPD is resolved.

Investigational vaccine and placebo will be administered in addition to standard of care.

- **Experimental design:** Phase IIB, randomised, observer-blind, placebo-controlled, multi-centric study with two parallel groups.
- **Duration of the study:** for each subject enrolled, the study will last approximately 15 months from Visit 1 up to study completion (Visit 8).
 - Epoch 001: Screening Visit (Day -28 to Day -1).
 - Epoch 002 : Primary starting at Visit 1 (Day 1) and ending at Visit 8 (Day 451).
- **Primary completion Date (PCD):** Last Subject Last Visit (LSLV) from Visit 8 (Day 451) or last visit/contact of Epoch 002.
- **Study groups:**
 - **10-10-3-AS:** Approximately 300 subjects receiving two doses of the AS01_E-adjuvanted GSK Biologicals' NTHi-Mcat investigational vaccine containing 10 µg of PD, 10 µg of PE-PilA, and 3.3 µg of UspA2.
 - **CONTROL:** Approximately 300 subjects receiving two doses of placebo (PBS).

CONFIDENTIAL

207489 (NTHI MCAT-002)

Statistical Analysis Plan Amendment 2 FDA Final Draft

The following group names will be used for the statistical analysis

Table 1 Study groups and epochs foreseen in the study

Group order in tables	Number of subjects	Group label in tables	Group definition for footnote
1	~300	10-10-3-AS	2 doses of AS01E-adjuvanted NTHI/Mcat vaccine containing 10 mcg of PD, PE-PiA and 3 mcg of UspA2

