2	~300	PLACEBO	2 doses of phosphate buffered solution

- **Sampling schedule:**

- **Blood samples for assessment of humoral immunogenicity** will be collected from all subjects at Visit 1 (Day 1), Visit 2 (Day 31), Visit 3 (Day 61), Visit 4 (Day 91), Visit 6 (Day 271), Visit 8 (Day 451) and at each AECOPD visit from first vaccination to study conclusion.
- **Blood samples for assessment of cell-mediated immunogenicity (CMI)** will be collected from all subjects in the CMI sub-cohort (approximately 60 subjects in each group) at Visit 1 (Day 1), Visit 4 (Day 91), Visit 6 (Day 271) and at Visit 8 (Day 451).
- **Blood samples for biomarkers** will be collected from all subjects at Visit 1 (Day 1), Visit 8 (Day 451) and at each AECOPD visit from first vaccination to study conclusion.
- **Blood sample for haematology profile** will only be collected at Visit 1.
- **Sputum samples for PCR (all subjects) and culture** (50% of subjects) will be collected from all subjects at Visit 1 (Day 1), Visit 4 (Day 91), Visit 5 (Day 181), Visit 6 (Day 271), Visit 7 (Day 361), Visit 8 (Day 451) and at each AECOPD visit from first vaccination to study conclusion.

Other assessments:

- **COPD symptoms:** All subjects will be asked to record COPD symptoms in their electronic Diary Card:
 - Daily in the morning throughout the study (including during AECOPD): **morning symptoms questionnaire**.
 - Daily in the evening throughout the study (including during AECOPD): **EXACT-PRO questionnaire**.
- **HRQOL assessments:**
 - All subjects will be asked to complete the COPD assessment test (CAT) at the Screening Visit (pre-Day 1), Visit 6 (Day 271), Visit 8 (Day 451) and at each AECOPD visit from first vaccination to study conclusion.
 - All subjects will be asked to complete St. George's Respiratory Questionnaire for COPD patients (SGRQ-C) at the Screening Visit (pre-Day 1), Visit 6 (Day 271), at Visit 8 (Day 451) and at each AECOPD visit from first vaccination to study conclusion.

CONFIDENTIAL

207489 (NTHI MCAT-002)

Statistical Analysis Plan Amendment 2 FDA Final Draft

Pre- and post-bronchodilator spirometry assessments will be done for all subjects at the Screening Visit (pre-Day 1), Visit 6 (Day 271) and at Visit 8 (Day 451).

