4.3. Tertiary endpoints**Sputum sample PCR:**

- Occurrence (presence and absence), bacterial load measured by PCR of NTHi and/or Mcat in sputum before first vaccination and at Day 91, Day 181, Day 271, Day 361 and Day 451 and at each AECOPD visit.
- Number of acquisitions and apparitions of NTHi and Mcat bacteria in sputum collected from Day 1 and from Day 91 and analysed by PCR.

Sputum sample culture:

- Occurrence (presence and absence), and semi-quantitative bacterial load measured in a subset of sputum sample by culture of NTHi and/or Mcat in sputum before first vaccination and at Day 91, Day 181, Day 271, Day 361 and Day 451 and at each AECOPD visit.

CONFIDENTIAL

207489 (NTHI MCAT-002)

Statistical Analysis Plan Amendment 2 FDA Final Draft

- Number of acquisitions and with apparitions of NTHi and Mcat bacteria in sputum collected from Day 1 and from Day 91 and analysed by culture.
- Rate of NTHi-associated and Mcat-associated, moderate and severe AECOPD.
- Rate of NTHi-associated and Mcat-associated any severity AECOPD.
- Rate of NTHi-associated and Mcat-associated AECOPD, by severity.
- Time to first moderate or severe NTHi-associated and/or Mcat-associated AECOPD.
- Time to first any NTHi-associated and rate Mcat-associated AECOPD.
- Time to first NTHi-associated and rate Mcat-associated AECOPD, by severity.
- Duration of each moderate and severe NTHi-associated and Mcat-associated AECOPD.
- Duration of NTHi-associated and/or Mcat-associated AECOPDs of any severity.
- Duration of NTHi-associated and/or Mcat-associated AECOPD, by severity.

QOL:

- Assessment of EXACT-PRO score, daily in the evening throughout the study, in all subjects.
- Assessment of CAT scores at Screening, Day 271 and Day 451, and from first vaccination to study conclusion for each AECOPD visit, in all subjects.
- Assessment of SGRQ-C score at Screening, Day 271 and Day 451, and from first vaccination to study conclusion for each AECOPD visit, in all subjects.
- Assessment of use of medication to treat (AE)COPD and healthcare utilization in all subjects throughout the study period.

Lung function:

- Assessment of FEV1% of predicted normal value at Screening, Day 271 and Day 451, in all subjects.

Biomarkers:

- Concentration of selected biomarkers (fibrinogen, hsCRP and IP-10), at Day 1 and Day 451, and for each AECOPD visit from first vaccination to study conclusion.

T helper profile:

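### Section 6.6.2 excludes subjects, not diary days or visits, for partial questionnaire data; this conflicts with its own EXACT-PRO averaging and 4-day baseline rule

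*SAP*

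**What the plan says.** Section 6.6.2 opens with one missing-data rule for every instrument in it: "For each of the following questionnaire missing items will not be imputed and subjects with partial data will be excluded". EXACT-PRO, CAT and SGRQ-C follow in that order.

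EXACT-PRO "constitutes of 14 items which are patient-reported outcome (PRO) via daily diary". Section 4.3 lists the endpoint as "Assessment of EXACT-PRO score, daily in the evening throughout the study, in all subjects", and Section 2 puts the study at about 15 months, ending at Day 451.

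The EXACT-PRO text in Section 6.6.2 then gives two rules of its own. On period scores: "For each subject the average score across all days, within each period is computed". On baseline: "If fewer than 4 days scores are available, the EXACT-PRO baseline score cannot be calculated". No minimum number of days is set for the treatment, exacerbation, follow-up or 3-month periods.

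CAT and SGRQ-C are collected at Screening, Day 271, Day 451 and every AECOPD visit.

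**The concern.** The opening rule names the subject as the unit to be dropped. For a diary the natural unit is the day; for CAT and SGRQ-C it is the single assessment. Averaging over days and accepting 4 days at baseline presuppose that a subject with gaps stays in. Dropping subjects with partial data presupposes the opposite. After baseline no other rule settles the matter, so two programmers could build different analysis sets from the same text.

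At stake is who enters the between-arm quality-of-life comparisons. These are tested at p<0.1 and, under Section 8, are released with the Priority 1 analyses in the full study report. If exclusion depends on how many forms a subject had to complete, it depends on the number of exacerbations, which is the primary outcome.

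**Working it through.** The SAP states no completion rate, retained number or power for EXACT-PRO, so there is no planned figure to reproduce. The rates below are assumptions, shown as ranges.

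**Inputs from the SAP.** 14 items per evening; Day 1 to Day 450 = 450 evenings; follow-up Day 91 to Day 450 = 360; each sub-period 90 (for example Day 91 to Day 180); about 600 subjects. A complete 450-day diary holds 14 × 450 = 6,300 item responses.

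**Step 1. A missed evening counts as partial data (strict reading).** With daily completion p, equal across subjects and independent between days, the share kept over D days is p^D.

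| p | D = 90 | D = 360 | D = 450 |
|---|---|---|---|
| 0.95 | 1.0% | 0.0% | 0.0% |
| 0.98 | 16.2% | 0.07% | 0.01% |
| 0.99 | 40.5% | 2.7% | 1.1% (about 7 of 600) |
| 0.995 | 63.7% | 16.5% | 10.5% (about 63) |
| 0.999 | 91.4% | 69.8% | 63.8% (about 383) |

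Keeping half the subjects over 450 days needs p of about 0.9985.

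**Step 2. Compliance differs between subjects.** If p follows a beta distribution, the 450-day share kept runs from under 0.1% (mean 0.80, a+b = 20), through 14% (mean 0.95, a+b = 10), to 80% (mean 0.98, a+b = 2).

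**Step 3. Only unanswered items in an opened diary count (narrow reading).** With q item gaps per day, the 450-day share kept is (1 − q)^450: 100% at q = 0, 96% at 0.0001, 64% at 0.001, 1% at 0.01.

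**Step 4. The baseline rule beside the exclusion rule.** With 7 screening days and p = 0.80, at least 4 scores are available for 96.7% of subjects. A complete-data rule keeps 0.80^7 = 21.0%. The two rules define very different sets.

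**Step 5. CAT and SGRQ-C.** A subject who completes follow-up fills in 3 scheduled forms per instrument, plus one per AECOPD visit. If each form is incomplete with probability r, independently, the share kept under the literal rule is (1 − r)^(3 + number of AECOPD visits).

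| r | No AECOPD | Three AECOPDs |
|---|---|---|
| 2% | 0.98^3 = 94% | 0.98^6 = 89% |
| 5% | 0.95^3 = 86% | 0.95^6 = 74% |
| 10% | 0.90^3 = 73% | 0.90^6 = 53% |

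The gap arises with the same completion rate per form in every subject.

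**Step 6. Other sections of the SAP.** For solicited events, also collected by e-diary, Section 11.2.6 keeps subjects whose daily recording is only partial. Section 11.2.5 ties its missing-data rule to a given measurement. Section 6.6.2 has neither qualifier.

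**The case against.** The strongest reply is that the sentence concerns unanswered items. An evening when the diary was never opened is an absent questionnaire, not a partial one. On that view the 4-day rule is the specific provision for missed days and shows that they do not exclude anyone. Excluding a subject would then mean excluding that subject from the analysis concerned, as the similar wording in Section 11.2.5 does, and CAT and SGRQ-C are in any case analysed time point by time point.

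Much of this stands. It is a sensible reading and may be what was intended. It also defeats a stronger inference that a reader might draw from Step 1, that the rule removes nearly all subjects and leaves only perfect compliers. That inference needs missed evenings to count as partial data, which the 4-day rule speaks against. It also needs the rule to run over the whole study, although scores are analysed by period, and a completion rate that the SAP does not give.

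A reader might likewise infer that diary gaps cluster in severe exacerbations or hospital stays. The SAP says nothing on that; Section 2 plans diary completion during exacerbations too.

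The reply does not remove the defect. Even on the narrow reading, one unanswered item among 6,300 excludes the subject as the sentence is worded. Missed days after baseline are then left with no minimum. Nothing in Section 6.6.2 confines the exclusion to the visit concerned.

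**Conclusion.** The point holds as a conflict within Section 6.6.2: a subject-level exclusion set against day-level averaging and a baseline that tolerates missed days. Its size cannot be fixed from the SAP. Depending on the reading and on assumed completion, the 450-day loss ranges from almost none to nearly everyone. The direction of one effect is clearer: under the literal rule, subjects with more AECOPDs complete more CAT and SGRQ-C forms and are likelier to be dropped. Exclusion can therefore differ by arm if exacerbation rates do. That mechanism does not apply to EXACT-PRO, where every subject has the same evening schedule.

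Only exploratory, multiplicity-unadjusted quality-of-life comparisons are affected; the primary endpoint is not. The wording should be corrected, but this is not a threat to the trial's main conclusion.

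**What to change.** Replace the opening sentence of Section 6.6.2 with:

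> Missing items are not imputed. An EXACT-PRO day, or a CAT or SGRQ-C assessment, with missing items is excluded for that day or visit only, and the subject's other data are kept. Missed diary days do not exclude a subject.

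Pre-specify a minimum number or proportion of scored days for each post-baseline EXACT-PRO period, scaled to its length. Carrying over the flat 4 days from baseline would be too thin: 4 of 90 days is 4.4% of a sub-period and 4 of 360 is 1.1% of follow-up. Tabulate diary completion by arm and period.

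The cost is SAP wording and one table. The downside is that period means will rest on differing numbers of days, which the completion table makes visible.

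### The EXACT-PRO between-group test in the Exacerbation period compares only subjects who had an AECOPD, a subset the vaccine itself can change

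*SAP*

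**What the plan says.** The EXACT-PRO part of SAP section 6.6.2 (Amendment 2) begins: "All EXACT-pro scores will be divided in to the following periods". The periods are Screening, Treatment, Exacerbation and Follow-up, the last also cut into four three-month sub-periods. The Exacerbation period is defined as "Exacerbation: scores collected during the start date of an exacerbation until resolution".

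The unit of analysis is a subject mean: "For each subject the average score across all days, within each period is computed". The between-group rule is "At each period and sub period the two groups will be compared using an ANCOVA model", with the screening score as covariate and treatment as factor. No period is excepted.

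The opening of section 6.6.2 sets the standard of evidence: "The following analysis are exploratory and a p-value <0.1 will be considered statistically significant". It adds: "All comparisons should be interpreted with caution considering that there will be no adjustment for multiplicity". On incomplete questionnaires it says that "missing items will not be imputed and subjects with partial data will be excluded".

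In the same section, CAT and SGRQ-C scores at AECOPD visits are only tabulated by number and severity of events. Their between-group tests are limited to scheduled time points.

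**The concern.** A subject who never exacerbates has no days in the Exacerbation period, so has no mean and drops out of that ANCOVA. Entry to the test therefore depends on an outcome observed after randomisation. By the primary objective (section 3.1), it is the outcome the vaccine is intended to alter. Which subjects enter, and which kinds of event make up their means, can then differ between arms for reasons unrelated to how bad any given event is.

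If the vaccine mainly prevents milder events, the events left in that arm are worse on average and the test suggests harm. If it mainly prevents the worse ones, the test suggests that individual AECOPDs became milder. Neither is an effect on symptoms in the randomised population. The screening score cannot correct this, because the selection acts on which events occur and not on where subjects started.

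The quality-of-life objective belongs to the Priority 1 analyses that go into the full clinical study report (section 8), so the p-value will be reported prominently.

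**Working it through.** **Inputs from the SAP.** About 300 subjects per arm (section 2), allocation 1:1 (section 11.3), and the ANCOVA terms and p<0.1 rule (section 6.6.2). The SAP states no event rate, EXACT-PRO mean or SD, or power figure for this comparison, so there is no figure of its own to reproduce.

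**Assumptions.** 290 evaluable subjects per arm; 1.4 to 2.0 AECOPDs of any severity per year; negative binomial dispersion k of 0.5 to 1.0; mean score 45 in mild and 55 in moderate or severe events, with higher meaning worse; subject SD 10; a two-sided test; and no vaccine effect on the score of any event that still occurs.

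**Step 1: share without a score.** P(no event) = (1 + kμ)^(-1/k).
- μ = 2.0, k = 0.5: (1 + 1.0)^(-2) = 0.25.
- μ = 1.4, k = 1.0: (1 + 1.4)^(-1) = 0.42.

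So 25-42% of subjects drop out of the test over one year. Over 15 months (μ × 1.25) the figures are 2.25^(-2) = 0.20 and 2.75^(-1) = 0.36.

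**Step 2: shift caused by event mix alone.** With half the events mild, the mean is 50 in placebo.
- 30% of mild events prevented: the mild share becomes 0.7/1.7 = 0.412, the mean 55 - 10 × 0.412 = 50.88, the shift **+0.88**.
- 30% of moderate or severe events prevented: the mild share becomes 1/1.7 = 0.588, the mean 49.12, the shift **-0.88**.
- With only 30% of events mild (placebo mean 52), the same reductions give 0.21/0.91 = 0.231, shift +0.69, and 0.30/0.79 = 0.380, shift -0.80.
- Equal proportional reduction of both types leaves the mix unchanged: shift 0.

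**Step 3: compare with the standard error.** SE = 10 × √(2/(290 × share with an event)).
- Share 0.75: 10 × √(2/217.5) = 0.96, so 0.88/0.96 = 0.92 SE.
- Share 0.583: 10 × √(2/169.2) = 1.09, so 0.88/1.09 = 0.81 SE.

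At two-sided 0.1 (cut-off 1.645), a shift of 0.81-0.92 SE gives rejection in that direction in about 20-23% of trials, against 5% nominal.

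**Step 4: simulation with other, stronger assumptions.** 300 per arm; 1.0, 1.5 or 2.5 events per placebo subject; k = 1; half the events adding 6 points and half adding 14; residual SD 6; baseline mean 40, SD 10; 1,000 trials per scenario. The vaccine only removes events. About 150, 180 and 214 of 300 placebo subjects enter the test at the three rates.

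| Events prevented | Exacerbation-period difference (vaccine - placebo) | Significant at p<0.1 | All subjects, whole follow-up |
|---|---|---|---|
| None | about 0 | 9-10% in total | about 0 |
| 25% of both types | about 0 | about 10% in total | -0.09 to -0.22 |
| 40% of milder | about +1.0 | vaccine worse in 34-44% | -0.05 to -0.12 |
| 50% of milder, 10% of worse | +1.15 to +1.19 | vaccine worse in 42-54% | -0.10 to -0.19 |
| 40% of worse | about -1.0 | vaccine better in 36-47% | -0.07 to -0.23 |

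The last column averages the daily score over 360 days in all subjects, at 12 days per event. It has the right sign in every row where events are prevented. The Exacerbation-period test has the wrong sign in two of those rows and shows nothing in a third.

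**The case against.** **Scope of the test.** The ANCOVA rule cannot be wholly literal: applied to Screening, the outcome would be its own covariate. The sentence just before it separates stable periods from exacerbations, so the test might be meant for stable periods only. This shows that the wording is loose. Nothing in the text excepts Exacerbation, however. Template 48 in the superseded SAP versions carries a difference column and a p-value row for that period; this is corroboration only, and the same template has a p-value row for Screening. Either way, one sentence needs changing.

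**Weight.** The endpoint is tertiary, labelled exploratory, and enters no success criterion. That stands and keeps the point minor. The caution in section 6.6.2 concerns multiplicity, though, and says nothing about selection.

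**Interpretation.** The row would be labelled Exacerbation with its own N, so the restriction is visible, and the average severity of the events that remain is a legitimate description. Section 6.3 itself lists reduced AECOPD severity as an aspect of efficacy. This is fair, and it supports descriptive reporting. It does not support a between-arm p-value read as a treatment effect.

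**Direction and size.** A wrong-way result needs preferential prevention of milder events, which the SAP gives no reason to expect, and every score and rate above is assumed. Both points stand.

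**Conclusion.** The concern holds as a minor point. As written, the plan tests the arms at p<0.1 in a subset defined by an event the vaccine is meant to prevent, and the result can favour the wrong arm. It is unbiased if the vaccine does not alter occurrence, and blind to benefit if all event types fall equally.

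On the assumptions of Steps 1 to 3, the artefact is about 0.7 to 0.9 points in either direction; with an even event mix it is 0.8-0.9 SE. The larger simulated error rates rest on stronger assumed effects. All of this assumes that a higher EXACT-PRO score is worse, which the SAP does not state. The primary conclusion is untouched.

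**What to change.** In section 6.6.2, limit the between-group ANCOVA to the Treatment and Follow-up periods and the Follow-up sub-periods. Report Exacerbation-period scores descriptively by arm and AECOPD severity without a between-arm p-value, matching the treatment of CAT and SGRQ-C at AECOPD visits.

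State also that the Follow-up mean includes exacerbation days. The present definition does not remove them, but dividing the scores into periods that include Exacerbation leaves this open. If they were removed, the Follow-up comparison would omit the symptom burden of exacerbations.

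The cost is a wording change and one p-value that is hard to interpret. No new data are needed. The Follow-up contrast is diluted by stable days: in the simulation it was 0.05 to 0.23 points against an SE of about 6 × √(2/300) = 0.49. It should be presented as an estimate with its interval and not expected to reach significance.
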